3.5 Effectiveness Assessments

The primary effectiveness variable is the proportion of patients achieving a $\geq 0.5 \log_{10}$ decrease from Baseline in viral load at Day 7 (assessed for Cohort 2 only).

Secondary effectiveness variables will be the following:

- Proportion of patients with HIV-1 RNA levels < 50 copies/mL and < 400 copies/mL at assessment time points (assessed for Cohort 2 only)
- Mean change from Baseline in viral load at Day 7 and all assessment time points (assessed for Cohort 2 only)
- Proportion of patients achieving a $\geq 0.5 \log_{10}$ and $\geq 1.0 \log_{10}$ decrease from Baseline in viral load at all assessment time points (assessed for Cohort 2 only)
- HIV-1 sensitivity/susceptibility changes associated with virologic failure after administration of ibalizumab

3.6 Safety Assessments

Safety assessments will include the results of the following measurements throughout the study:

- Physical examinations
- Vital sign measurements
- Clinical laboratory parameters (hematology, serum chemistry, and urinalysis)
- Monitoring of AEs and concomitant medications
- Incidence of Class C events as defined by the Centers for Disease Control and Prevention (CDC) Classification System for HIV Infection (Appendix A)
- Anti-ibalizumab antibody levels (immunogenicity of ibalizumab)

4. Study Treatments

4.1 Study Drug Dosage and Administration

There are two different ibalizumab IV drug product vial configurations available for use in this study:

Current Drug Lots In Use

(1) vials with a 1.33 mL injection volume and 200 mg ibalizumab per vial (Lots 201509019 and 201505012).

Patients receiving ibalizumab in study TMB-301, who will enroll into Cohort 1 of this study, and patients initiating ibalizumab in Cohort 2 will receive only vials with a 1.33 mL injection volume and 200 mg ibalizumab per vial.

Previous Drug Lot that is Depleted

(2) vials with a 1.2 mL injection volume and 180 mg ibalizumab per vial (Lot 201403001. This information is provided only in the event that Cohort 1 sites, with patients who were previously under Investigator sponsored IND protocols, may still have this lot in their inventory).

All ibalizumab drug product to be used in this study will be at a concentration of 150 mg/mL.

4.1.1 Cohort 1

Patients in Cohort 1 will continue receiving ibalizumab via IV infusion at the currently assigned dosage: either 800 mg q2wk or 2,000 mg q4wk.

(Lots 201509019 and 201505012)

For patients enrolling into this study from study TMB-301, study drug will be provided in open-labeled cartons of 10 vials at 1.33 mL/200 mg each. For the 800 mg q2wk doses, 4 vials are to be

used. Using a sterile syringe, 1.33 mL is withdrawn from each of the vials to be used and injected into a 250 mL infusion bag of normal saline. Administration of the prepared infusion should begin no more than 6 hours after the time of preparation.

(Lot 201403001)

Until the supply of drug product currently allocated for use in Cohort 1 patients enrolling from Investigator-sponsored INDs is exhausted, study drugs for these patients will continue to be provided in open-labeled cartons containing 10 vials at 1.2 mL/180 mg each.

- For the 2,000 mg q4wk doses (adjusted to 2,010 mg for this vial configuration), 13.4 mL total volume of ibalizumab drug product is required for each administration.
- For the 800 mg q2wk doses (adjusted to 810 mg for this vial configuration), 5.4 mL total volume of ibalizumab drug product is required for each administration.

Using a sterile syringe, the required content is withdrawn from each of the vials to be used and injected into a 250 mL infusion bag of normal saline. Administration of the prepared infusion should begin no more than 6 hours after the time of preparation.

When the 1.2 mL, 180 mg/vial drug product is exhausted, patients enrolled in Cohort 1 from Investigator-sponsored INDs will be switched to the 1.33 mL, 200 mg/vial drug product. Study drug will then be provided in open-labeled cartons of 10 vials at 1.33 mL/200 mg each.

- For the 2,000 mg q4wk doses, all 10 vials in a carton are to be used.
- For the 800 mg q2wk doses, 4 vials are to be used.

Using a sterile syringe, 1.33 mL is withdrawn from each of the vials to be used and injected into a 250 mL infusion bag of normal saline. Administration of the prepared infusion should begin no more than 6 hours after the time of preparation.

4.1.2 Cohort 2

(Lots 201509019 and 201505012)

Study drug will be administered via IV infusion at a dose of 2,000 mg on one occasion (Day 0/Baseline), followed 2 weeks later (Day 14) by doses of 800 mg administered once every 2 weeks through the remainder of the study.

Study drug will be provided in open-labeled cartons of 10 vials each.

- For the 2,000 mg doses, all 10 vials in a carton are to be used.
- For the 800 mg doses, four vials are to be used.

Using a sterile syringe, 1.33 mL is withdrawn from each of the vials to be used and injected into a 250 mL infusion bag of normal saline. Administration of the prepared infusion should begin no more than 6 hours after the time of preparation.

4.1.3 Administration

The infusion should be administered in the cephalic vein of the patient's right or left arm. If this vein is not accessible, an appropriate vein located elsewhere can be used. For patients initiating ibalizumab in Cohort 2, the duration of the infusion should be no less than 30 minutes during the first two study drug administrations. If no infusion-associated AEs have occurred after two administrations, the duration of the infusion can be decreased to no less than 15 minutes.

The start and stop times of each infusion will be recorded in an Electronic Data Capture (EDC) system, along with the site of administration. The date of use and the patient's study identification (ID) number and initials will be recorded.

All Cohort 2 patients must be observed for 1 hour after completion of study drug administration for at least the first two administrations (Day 0/Baseline and Day 14). If the patient does not experience an AE(s) related to the infusion (local or systemic) during the first two infusions, then the post-infusion observation time can be reduced to 15 minutes thereafter.

In addition to the study drug, all patients will receive an OBR, which is a standard-of-care regimen selected by the investigator based upon treatment history and the results of recent viral resistance testing. For patients enrolling into Cohort 2, previous resistance testing done within 6 months prior to Screening must demonstrate that the patient's viral isolate is sensitive/susceptible to a minimum of one of the agents selected for the OBR. As part of the OBR, the patient must be willing and able to take at least one of the agents to which their virus is sensitive/susceptible.

4.2 Prohibited Medications and Restrictions

Use of and changes in concomitant medications will be recorded in the patient's source documents and the EDC system. All prescription drugs, herbal products, vitamins, minerals, and over-the-counter medications are to be recorded.

Any concomitant medication, with the exception of those listed in Section 4.4.2 for Cohort 2 patients, may be given at the discretion of the investigator. However, the investigator has the responsibility of ensuring that details regarding the concomitant medication are recorded for the patient in the EDC system. Complete information is expected for any medication prescribed during the trial.

The prescribing information for all concomitant medications should be reviewed carefully. The guidance provided in the respective contraindications, warnings, and precautions section for any medication must be followed to prevent any potentially serious or life-threatening drug interactions.

For patients enrolled into Cohort 2 only, the following medications are not to be administered concomitantly:

- Therapeutic HIV vaccines from Screening until study participation ends
- Any vaccines during the 7 days before Day 0/Baseline through Day 14 of the study
- All investigational drugs from 30 days before Day 0/Baseline and throughout the study (except investigational antiretroviral medications as a component of the OBR)

In addition, radiation therapy is not allowed for patients in Cohort 2 from 28 days before first administration of study drug to the last administration of study drug. Patients receiving radiation therapy are not allowed to enter Cohort 2 of the study; however, if a patient in Cohort 2 develops a condition that requires radiation but does not disqualify them from study participation for any other reason, then this event would need to be discussed with the medical monitor.

First-dose, generalized, self-limiting skin rash has been described with therapeutic MAbs.^{5,6} Re-challenge in such an event is at the discretion of the investigator. While there is no recommendation for premedication with diphenhydramine, acetaminophen, or corticosteroids, these medications have been used prior to the administration of other MAbs.⁷ Any patient who experiences anaphylactoid symptoms that are considered to be related to the study drug (possibly, probably, definitely) must have study drug discontinued and be withdrawn from the study immediately. Severe post-infusion reaction management typically includes corticosteroids, oxygen, and IV fluids, based on the severity and symptoms.⁷ Refer to Appendix C for further information on the management of suspected anaphylactoid reactions. Study drug should only be administered in a setting that allows for rapid

access to emergency cardiopulmonary support services in the event of a life-threatening infusion-related AE (e.g., anaphylaxis).

4.3 Measurement of Patient Adherence

Patient adherence will require the availability of the patient at the study site to receive the dose and the patient's willingness/ability to receive the entire dose. The receipt of the entire dose is assured, as each dose is given as an IV infusion by a trained professional from the clinical site and the event is recorded. Adherence to the OBR will also be recorded.

4.4 Missed Doses of Study Drug

4.4.1 Cohort 1

Patients should receive study drug per the Schedule of Events (Section 3.4). A missed dose is defined as any dose of study drug that is not administered within the study visit window. Patients who miss doses of study medication for two consecutive dosing intervals (i.e., >28 days without a study drug infusion) of 800 mg dosage or one and one-half dosing intervals (i.e., >42 days without a study drug infusion) of the 2,000 mg dose may be withdrawn from the study.

Missed Doses. If a dose is missed, the missed dose should be administered at the first opportunity. If an 800 mg dose is missed and cannot be administered at least 3 days before the next scheduled dose, it should be skipped. If a 2,000 mg dose is missed and cannot be administered at least 5 days before the next scheduled dose, it should be skipped.

End of study (EOS) procedures should be performed as soon as possible after the patient qualifies for withdrawal due to missed doses. Patients who are withdrawn from the study for missed doses may not be permitted to participate in other ibalizumab protocols.

4.4.2 Cohort 2

Patients should receive study drug per the Schedule of Events (Section 3.4). A missed dose is defined as any dose of study drug that is not administered within the study visit window. Patients who miss doses of study medication for two consecutive dosing intervals (i.e., >28 days without a study drug infusion) or miss greater than two doses cumulatively will be withdrawn from the study. EOS procedures should be performed as soon as possible after the patient qualifies for withdrawal due to missed doses. Patients who are withdrawn from the study for missed doses may not be permitted to participate in other ibalizumab protocols.

Missed Initial (Loading) Dose. If the initial 2,000 mg dose (loading dose) of study drug is administered outside the treatment window, the dose should be administered at the first available opportunity and the timing of subsequent doses should be adjusted to coincide with the actual administration time of the first dose.

Missed Maintenance Dose (3-7 days). If a dose of 800 mg (maintenance dose) of study drug is missed by going beyond the scheduled dosing day by 3-7 days, a loading dose of 2,000 mg (reload) should be administered at the next available opportunity. The reload dose would substitute for the maintenance dose that was missed. All other visit procedures would not change other than the dose amount administered (i.e., 2,000 mg reload dose substituted for 800 mg maintenance dose). The scheduling of subsequent visits will not be adjusted.

Example: If a patient is scheduled to receive study drug on Day 49 (Week 7) but cannot come in until Day 55, the patient should receive a 2,000 mg loading dose (reload) on Day 55. The subsequent dose should be 800 mg and scheduled for Day 63 (Week 9) (± 2 day window). The patient should continue on the original visit schedule.

Missed Maintenance Dose (>7 days and <14 days). If a dose of 800 mg (maintenance dose) of study drug is missed by going beyond the scheduled dosing day by more than 7 days but less than 14 days, the patient should receive a 2,000 mg dose (reload) at the next available opportunity. The missed dose should be recorded as a missed dose/missed visit. A 2,000 mg reload dose administered between >7 days and <14 days beyond the scheduled dosing date will not substitute for the missed dose. The 2,000 mg reload dose will substitute for the next scheduled 800 mg maintenance dose. Study procedures for the visit subsequent to the missed dose/missed visit should be performed along with the administration of the 2,000 mg reload dose. The dosing schedule should be adjusted

such that the following 800 mg maintenance dose should be scheduled 2 weeks after the reload dose was administered. NOTE: Week 102/EOS procedures should be performed without regard to dose window whenever the visit occurs.

Example: If a patient is scheduled to receive study drug on Day 49 (Week 7) but cannot come in until Day 58, the patient should receive a 2,000 mg loading dose (reload) on Day 58. Study procedures for Day 49 (Week 7) are recorded as missed. Study procedures for Day 63 (Week 9) are performed along with the administration of the 2,000 mg reload dose. The dose following the reload dose should be 800mg and scheduled for Day 72 (± 2 day window). The visit schedule would be adjusted to 800 mg every 2 weeks from the day the drug was actually administered.

No adjustments to dosage or dosing schedules are required for a missed dose that occurs before the dosing window. However, any dose administered before the dosing window is also considered a missed dose.

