6.3.3 Events for Day 7 (± 1 day)

Day 7 serves as the time point at which the antiviral activity of ibalizumab will be assessed to address the primary effectiveness objective of the study.

Site personnel will undertake the following:

- Assess adherence to the OBR
- Record results of abbreviated physical examination
- Record vital sign measurements, AEs, and concomitant medications
- Collect blood and urine samples for the following:
 - Clinical laboratory assessments (serum chemistry, hematology, and urinalysis; see [Section 7.2.2](#) for a complete list of parameters)
 - Archive sample
 - HIV-1 RNA (viral load)
 - HIV-1 viral resistance sample (will be stored for later use if needed)
 - CD4⁺ cell count

6.3.4 Events for Day 14 (± 1 day), and Weeks 4, 6, 8, 10, 14, 16, 18, 20, 22, 26, 30, 32, 34, 38, 40, 42, 44, 46, 50, 52, 54, 56, 58, 62, 64, 66, 68, 70, 74, 76, 78, 80, 82, 86, 88, 90, 92, 94, 98, 100, 102, 104, 106, 110, 112, 114, 116, 118, 122, 124, 126, 128, 130, 134, 136, 138, 140, and 142 (± 2 days)

The following will be completed before study drug administration:

- Record results of physical examination (complete exam at Week 4 only, abbreviated exam at Weeks 20, 32, and 40 only)
- Record the patient's weight (Weeks 4, 20, 32, and 40 only)
- Record vital sign measurements
- Record AEs and concomitant medications
- Assess adherence to the OBR (Weeks 4, 8, 20, 32, and 40 only)
- Collect urine and perform pregnancy test for females of childbearing potential (Weeks 4, 8, 16, 20, 32, 40, 44, 52, 56, 64, 68, 76, 80, 88, 92, 100, 104, 112, 116, 124, 128, 136, and 140 only)
- Collect blood samples for the following:
 - HIV-1 RNA (viral load) (Day 14, and Weeks 4, 6, 8, 16, and 20 only)
 - HIV-1 viral resistance sample (will be stored for later use if needed) (Day 14, and Weeks 4, 6, 8, 16, and 20 only)
 - CD4⁺ cell count (Day 14, and Weeks 4, 6, 8, 16, and 20 only)

Site personnel will undertake the following after administration of study drug (800 mg):

- Record vital sign measurements after completion of infusion and observe patient for at least 1 hour; if the patient did not experience an AE(s) related to the infusion (local or systemic) through and including the infusion on Day 14, then the observation time can be reduced to 15 minutes
- Record AEs

6.3.5 Events for Weeks 12, 24, 48, 60, 72, 84, 96, 108, 120, 132, and 144/EOS (± 2 days)

Site personnel will undertake the following before administration of study drug:

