- Record results of physical examination (complete exam at Week 24, 48, 72, 96, 120, and 144 only ; abbreviated exam at Weeks 12, 60, and 84 only)
- Record the patient's weight (Weeks 12, 24, 48, 60, 72, 84, 96, 120, and 144 only)
- Record vital sign measurements
- Record AEs and concomitant medications
- Assess adherence to the OBR
- Collect blood and/or urine samples for the following:
 - Hepatitis serology and C-reactive protein (Weeks 24, 48, and 96, only)
 - Clinical laboratory assessments (serum chemistry, hematology, and urinalysis; see [Section 7.2.2](#) for a complete list of parameters) (Weeks 12, 24, 48, 60, 72, 84, 96, and 120 only)
 - Archive sample (Weeks 12, 24, 48, 60, 72, 84, 96, 120, and 144 only)
 - Pregnancy test for females of childbearing potential (serum at Weeks 24, 48, 72, and 96 only; urine at all other listed weeks)
 - HIV-1 RNA (viral load)
 - HIV-1 viral resistance sample (will be stored for later use if needed)
 -
 - CD4⁺ cell count (within 1 hour before the start of the infusion)
 - Immunogenicity of ibalizumab (Weeks 24, 48, 72, 96, , 120, and 144 only)

Site personnel will undertake the following after administration of study drug (800 mg):

- Record vital sign measurements after completion of infusion and observe patient for at least 1 hour; if the patient did not experience an AE(s) related to the infusion (local or systemic) through and including the second infusion on Day 14, then the observation time can be reduced to 15 minutes

- Record AEs

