## 3.3.4. Missing Data Conventions

Cohort 2 patients with missing data at Day 0 will use the Screening visit value as their Day 0 result. Similarly, patients with missing data at Screening will use the Day 0 visit value as their Screening result. No Screening or Day 0 data will be imputed for Cohort 1 patients.

Unless otherwise specified, missing data for subsequent visits will be considered missing at random and will not be imputed. If necessary, imputation of partial dates may be performed during the data analysis and will be documented (e.g., missing month=July; missing day=15).

The **Missing Equals Failure (MEF)** imputation technique will be applied to the viral load measures (log10 copies/mL and copies/mL) only. If a viral load measurement is missing at any scheduled visit, the value will be replaced with the baseline viral load measurement. Also, all visits after a confirmed virologic failure will be imputed as failures (replaced with the baseline measurement) for all study visits even if the patient discontinued early.

The Last Observation Carried Forward (LOCF) imputation technique will be applied to the CD4+ T-Cell Counts (cells/mm^3) only. If a CD4+ T-Cell Count is missing at any scheduled visit, the value will be replaced with the most recent previous non-missing value.

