## 4.5.2.3 Virologic Outcome

## Snapshot Approach

Virologic outcome will be assigned for each patient at each key visit after Week 12 [Weeks 24, 48, 72, 96, 120, and 144/EOS], per the snapshot approach, using the following standard categories:

- 1=Virologic success (≥0.5 log10 decline from Baseline in viral load)
- 2a=(<0.5 log10 copies/mL drop from Baseline in viral load)
- 2b=Discontinued efficacy portion of study because of virologic failure (may still continue safety)
- 2c=Discontinued because of other reasons and the drop from baseline in viral load at the time of discontinuation was <0.5 log10 copies/mL
- 2d=OBR changed
- 3a=Discontinued because of AE or death
- 3b=Discontinued because of other reasons and the drop from baseline in viral load at the time of discontinuation was >=0.5 log10 copies/mL
- 3c=Missing data during the window but on study

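### When a Cohort 2 patient attends 8 to 13 days late, the samples due at five of the six key visits after Week 12 are not drawn, and the SAP then substitutes Baseline for the viral load

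*Protocol*

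**What the plan says.** Protocol 4.4.2 sorts late Cohort 2 maintenance doses by delay. At 3 to 7 days, the visit keeps all its own procedures. At more than 7 but less than 14 days, the rule changes: "The missed dose should be recorded as a missed dose/missed visit". What is done at the late attendance is then set by "Study procedures for the visit subsequent to the missed dose/missed visit should be performed along with the administration of the 2,000 mg reload dose". The worked example has the patient in clinic on Day 58 for a Day 49 visit and states: "Study procedures for Day 49 (Week 7) are recorded as missed". One exception is given: "NOTE: Week 102/EOS procedures should be performed without regard to dose window whenever the visit occurs".

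The sampling schedule is in Table 3-6 and Protocol 6.3.4 to 6.3.7. At the in-between visits of 6.3.4, the entry is "HIV-1 RNA (viral load) (Day 14, and Weeks 4, 6, 8, 16, and 20 only"). Within the 6.3.5 visits, safety laboratories are taken at "Weeks 12, 24, 48, 60, 72, 84, 96, and 120 only". Weeks 28, 36 and 150 add to these.

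SAP 3.3.1 analyses by the nominal visit on the eCRF. SAP 3.3.4 states: "If a viral load measurement is missing at any scheduled visit, the value will be replaced with the baseline viral load measurement". CD4+ counts are carried forward, and other missing data are not imputed. The snapshot section fixes the visits that matter: "Virologic outcome will be assigned for each patient at each key visit after Week 12 [Weeks 24, 48, 72, 96, 120, and 144/EOS"].

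**The concern.** Scoring a missing viral load as failure is a conservative convention for data that could not be obtained. Here the plan itself creates the gap. The patient is on site, has not yet been infused and remains on study, but the rule calls for a different visit's procedures, and those contain no samples. A patient 7 days late for Week 48 has the Week 48 samples drawn, while one 8 days late has none. The analysis then turns the late arrival into a non-response.

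At stake are the secondary efficacy estimates at the SAP's key visits, and scheduled laboratory and antibody results in a study whose primary objectives include safety. Viral load and CD4+ counts also feed the definitions of virologic failure and of CD4+ toxicity.

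**Working it through.** **Step 1. The band and the patient's status.** Inputs: Protocol 4.4.2 and its example. Delay: 58 − 49 = 9 days, inside the band. Next dose: 58 + 14 = Day 72, which is the protocol's own date. If the previous dose was on its day, the time since the last infusion is 14 + 8 = 22 to 14 + 13 = 27 days. The withdrawal rule for more than 28 days is not met, so the patient stays on study. (The example uses Weeks 7 and 9, which are not Cohort 2 visits, so it does not show what happens at a sampling visit.)

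**Step 2. Does the next visit recover the sample?** Viral load visits from Day 14 on: Day 14 and Weeks 4, 6, 8, 12, 16, 20, 24, 28, 36, 48, 60, 72, 84, 96, 108, 120, 132 and 144, which is 19 visits. Setting aside Week 144, which the NOTE exempts if it is read as applying to EOS, 18 remain.
- Followed two weeks later by another viral load: Day 14 and Weeks 4 and 6 (3 of 18).
- Not followed by one: all from Week 8 on (15 of 18).
- Weeks 26, 50, 74, 98 and 122, which follow the exposed key visits, have no viral load, CD4+, resistance, antibody, safety laboratory or archive sample.

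Key visits exposed: 5 of 6 after Week 12. From Week 38 to Week 142 there are (142 − 38)/2 + 1 = 53 dosing visits, and 8 of them carry a viral load.

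**Step 3. Nominal gaps if one key visit is lost (weeks).**

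| Lost visit | Viral load and CD4+ | Safety laboratories | Antibodies |
|---|---|---|---|
| 24 | 20→28: 8 | 12→28: 16 | 0→48: 48 |
| 48 | 36→60: 24 | 36→60: 24 | 24→72: 48 |
| 72 | 60→84: 24 | 60→84: 24 | 48→96: 48 |
| 96 | 84→108: 24 | 84→120: 36 | 72→120: 48 |
| 120 | 108→132: 24 | 96→150: 54 | 96→144: 48 |

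The schedule restarts from the late dose, which stands in for the next one. Calendar gaps are therefore 14 − 13 = 1 to 14 − 8 = 6 days shorter than shown.

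**Step 4. What the substitution does.** Value = Baseline, so change = 0. The patient fails both the 0.5 and the 1.0 log10 criteria and enters the mean change as zero. Cohort 2 entry requires more than 1,000 copies/mL, so a Baseline value will normally fail <50 and <400 copies/mL as well.

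**Step 5. Size.** One lost responder lowers a visit's rate by 100/n points: 1 point at n = 100 or 2 points at n = 50. (The anticipated 100 covers both cohorts.)

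The documents give no frequency for this lateness, but Protocol 4.4.2 withdraws a Cohort 2 patient who misses more than two doses in total. Maintenance doses from Day 14 to Week 144 number 72. A completer who used both misses in this band would average 2/72 = 2.8% per visit. Even if every such patient would have responded, the average loss is at most 2.8 points. As an illustration, with the 43% below 50 copies/mL that the protocol reports for TMB-301, the rate would become 43% × 70/72 = 41.8%, a loss of 1.2 points.

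**The case against.** Several points on the other side stand.

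- **Primary endpoint.** Day 7 comes before any maintenance dose, so it is untouched. The study is descriptive, with no formal hypothesis test, and the substitution can only lower a response rate.
- **Size.** A reader might infer a bias of several points, for example 5% of patients late and 80% of them responders: 0.05 × 0.80 = 4.0 points. The documents do not support this. 5% exceeds the 2.8% average that the cap allows for completers. Doses 3 to 7 days late and doses given before the window also count towards the cap. No response rate is given for patients 22 to 27 days from their last infusion, and the protocol reports that single-dose reductions lasted 2 to 3 weeks.
- **Scored as failure everywhere.** A reader might infer this too. It is exact for the responder proportions and the mean change. The snapshot table has its own code 3c for missing data, although SAP 4.4 applies the failure imputation to the efficacy analyses and could turn the same visit into 2a. The protocol states the imputation for Day 7 only and plans an unimputed mITT analysis, which the SAP makes conditional.
- **Safety.** The primary safety variables are adverse events and discontinuations. Adverse events, vital signs and concomitant medications are still recorded at the late attendance. Unscheduled visits (6.5) and extra antibody samples (7.2.9) are allowed for cause, though not described as replacing a missed visit's samples.
- **A late sample is a different measurement.** At 8 to 13 days late it is well outside the ±2-day window and reflects a longer dosing gap. This is a reason to flag the value. It does not make Baseline a better substitute, and the protocol already accepts out-of-window sampling in the 3 to 7 day band and at EOS.

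**Conclusion.** The point holds as an avoidable loss of secondary efficacy and scheduled safety data in Cohort 2. Five of the six key visits after Week 12 are exposed. Losing one leaves 24 weeks between viral loads (Week 48, 72, 96 or 120), 48 weeks between antibody samples, and 54 weeks between safety laboratories if Week 120 is lost.

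The effect on response rates is small and runs against the drug. The 2.8% bound assumes that the withdrawal rule is applied without exceptions, that patients complete, and that misses are not concentrated on key visits; one visit could exceed it. No point estimate of bias can be given.

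Week 144 counts as exempt only if the NOTE applies to the current EOS. It still says Week 102 and must be reconciled with Week 144.

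**What to change.** **Protocol 4.4.2.** Add that when the missed visit carried scheduled samples or an examination, these are done at the late attendance before the infusion, in addition to the next visit's procedures. Record them under the missed visit with the actual date and the days since the last infusion. For Day 14 and Weeks 4 and 6, where the next visit also has a viral load, the text need only settle which label the sample takes. Reconcile the NOTE's week with the current EOS.

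**SAP 3.3.1 and 3.3.4.** Use the flagged observed value for that visit in place of the Baseline substitution, with a sensitivity table that keeps the substitution. State whether a missing key-visit value is snapshot code 3c or 2a. Reconcile the virologic outcome listing footnote, which assigns visits by study-day windows, with the nominal-visit rule.

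**Cost.** A short protocol amendment with IRB approval, a few SAP sentences, an eCRF label and flag, and one extra table. There is no extra visit, and the samples were already planned. The downside is that the sample is 8 to 13 days late and follows a longer dosing gap, which is why the flag and the sensitivity table are needed. Dose and dosing dates are not changed.
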